### Study design scheme

### Schedule of study procedures

Procedure/ Visit	Visit 1 (Day 1)	Visit 2 (Day 3)	Visit 3 (Day 6)	Visit 4* (Day 10)	Visit 5 (Day 14±1)
Informed consent	+				
Collection of complaints	+	+	+	+	
Medical history	+				
Physical examination	+	+	+	+	
ARVI symptoms registration	+				
Inclusion/exclusion criteria	+				
Concomitant therapy	+	+	+	+	+
Nasopharyngeal swabs for RT-PCR	+				
Randomization and prescription of study drug	+				
Study drug supply	+				
Antipyretics	+				
Study drug accountability, compliance assessment			+		
Diary supply	+				
Checking the correctness of filling the diary		+	+	+	
Diary return			+	+	
Evaluation of treatment safety	+	+	+	+	
Telephone survey					+

\* Visit 4 – unscheduled (additional), provided if the patient still experiences the ARVI symptoms/ complications

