### **Safety assessment**

- Presence and type of adverse events during the therapy, their severity, relation to investigational drug, outcomes.
- Dynamics of vital signs.

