Patients are observed up for 14 days (screening and randomization up to 1 day, therapy for 5 days, follow-up from 6 to 10 day; delayed telephone “visit” on day 14). During the observation period two visits are planned (at home or at the medical center) on day 3 (Visit 2) and day 6 (Visit 3). If patients still have any symptoms of ARVI/complications of ARVI, then an additional (unscheduled) Visit 4 is held on Day 10 of the observation (at the medical center). During Visits 2, 3 (4), doctors carry out an physical examination, record dynamics of ARVI symptoms and concomitant therapy, check patient’s diaries, which parents/adoptive parents return back at Visit 3 or 4. At Visit 3 (after 5 days of therapy), compliance with the treatment is additionally assessed. A “telephone visit” (Visit 5, Day 14 ± 1) is carried out to interview parents about the patient’s condition, presence/absence of complications, and possible use of antibiotics. During the study, symptomatic therapy and therapy for underlying chronic conditions are allowed with the exception of the drugs indicated in the section “Prohibited Concomitant Treatment”.

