### ***Treatment duration***

Ergoferon/Placebo treatment duration is 5 days.

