## Statistical Analyses

### *Samples*

*Total set:* all patients included in the study whose parents/adoptive parents signed the Informed Consent Form for the patient's participation in the study. All AEs will be considered throughout the study for this sample.

*Safety population:* all patients who received at least one dose of the test drug. This sample will be used to **analyze the study therapy safety**, since all the AEs detected in the patient after administration of the drug product will be recorded. The AEs registered in patients of the *Total set* sample from the moment of signing the Informed Consent Form, but before the test drug administration will not be taken into account when analyzing the study therapy safety.

*Full Analysis Set.* This sample includes all the enrolled patients, except for those who have experienced at least one of the following events:

- 1) non-compliance with inclusion / exclusion criteria ;
- 2) the patient has not taken a single dose of the study drug;
- 3) lack of any data of the patient following randomization.

This sample, the most consistent with the "Intention-to-treat" principle, will be used for the **Intention-to-treat analysis (ITT analysis) of the the study therapy efficacy**.

To fill in the missing data (indicators/options), the method "LOCF" (Last Observation Carried Forward)" will be applied.

*Per protocol set.* This sample includes all the patients who have received the complex therapy under the Protocol, completed all the scheduled visits and had no significant deviations from the Protocol. This sample will be used for the **Per Protocol analysis (PP- analysis) of the the study therapy efficacy**.

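### After Day 6 a safety evaluation is scheduled only for children with persisting ARVI symptoms or complications, while the analysis text sets no end date for counting adverse events

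*Combined protocol and SAP*

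**What the plan says.** Five parts of the combined protocol and SAP bear on this.

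- **Safety assessment** defines the endpoint as "Presence and type of adverse events during the therapy, their severity, relation to investigational drug, outcomes". Under Treatment duration, "Ergoferon/Placebo treatment duration is 5 days".
- **Schedule of study procedures** has a row "Evaluation of treatment safety" with marks at Visits 1, 2, 3 and 4 (Days 1, 3, 6 and 10) and none at Visit 5 (Day 14±1). The rows for complaints and physical examination follow the same pattern. Concomitant therapy is marked at all five visits. The footnote says that Visit 4 is "provided if the patient still experiences the ARVI symptoms/ complications".
- **Study design** gives the same rule: "If patients still have any symptoms of ARVI/complications of ARVI, then an additional (unscheduled) Visit 4 is held on Day 10". The Day 14 call asks every family how the child is, and about "presence/absence of complications, and possible use of antibiotics". Adverse events are not named. The diary is handed back at Visit 3 or 4.
- **Statistical Analyses, Samples** says for the Safety population that "all the AEs detected in the patient after administration of the drug product will be recorded", with no closing date. For the Total set it takes account of adverse events over the whole study.
- **Safety parameters** tabulates events recorded in the study by severity, seriousness and relationship, again with no window.

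**The concern.** Whether a child has an active safety check after Day 6 depends on whether the child is still ill or has a complication. That is closely related to the primary endpoint, on which the plan expects the arms to differ. If events are tabulated without an end date, the arm with more persisting illness has more opportunities for an event to be found and counted. A between-arm difference in event counts could then arise with identical true event rates, and it would favour whichever arm recovers faster.

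A second consequence concerns follow-up. The safety endpoint includes the outcome of each event. An event still open on Day 6 in a child without ARVI symptoms or complications does not trigger Visit 4, so no later safety evaluation is scheduled at which its outcome would be recorded.

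**Working it through.** **1. The adverse-event period in each section**

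| Section | Period implied | Same for every child? |
|---|---|---|
| Safety assessment | The 5 days of therapy | Yes; Visit 3 on Day 6 covers it |
| Schedule of study procedures | To Day 6, or to Day 10 if Visit 4 is held | No |
| Samples (Safety population) | From first dose, no end stated | Not in scheduled ascertainment |
| Samples (Total set) and Safety parameters | The whole study | Not in scheduled ascertainment |

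The sections give no common end date. Under the first row there is no imbalance. Under the last two rows, events found at Visit 4 are counted.

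**2. Size, from assumed Visit 4 attendance**

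The plan gives no attendance figure, so the shares here are assumptions. If f is the share attending Visit 4, the mean day of the last scheduled safety evaluation is 6 + 4f.

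- Placebo 30%, Ergoferon 20%: 6 + 4×0.30 = 7.2 and 6 + 4×0.20 = 6.8; ratio 7.2/6.8 = 1.059.
- Placebo 40%, Ergoferon 25%: 6 + 4×0.40 = 7.6 and 6 + 4×0.25 = 7.0; ratio 7.6/7.0 = 1.086.

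**3. Size, from the plan's expected effect**

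The sample-size section assumes a difference of 0.5 days and an SD of 1.3 days. Those inputs reproduce its own result: a two-sided two-sample t-test at 5% with 80% power needs 107.09, so 108 per group, and 216/0.75 = 288. The sample size is unaffected by this point.

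The further assumptions are mine: normally distributed recovery times, a placebo mean μ of 4 to 6 days, every child still ill at Day 6 attends Visit 4 and no one else does, and a constant event rate λ of 0.01 or 0.03 per day, equal in both arms. Then

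- f(placebo) = 1 − Φ((6 − μ)/1.3), and f(Ergoferon) = 1 − Φ((6 − (μ − 0.5))/1.3);
- probability of a counted event = (1 − f)(1 − e^(−6λ)) + f(1 − e^(−10λ)).

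| Placebo mean (days) | Still ill at Day 6, placebo / Ergoferon | Mean last evaluation (day), placebo / Ergoferon | Apparent event ratio, λ = 0.01 | λ = 0.03 |
|---|---|---|---|---|
| 4.0 | 6.2% / 2.7% | 6.25 / 6.11 | 1.022 | 1.020 |
| 5.0 | 22.1% / 12.4% | 6.88 / 6.50 | 1.057 | 1.052 |
| 6.0 | 50% / 35% | 8.0 / 7.4 | 1.078 | 1.071 |

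With 144 children per arm, the smallest case is 144 × (0.0605 − 0.0592) ≈ 0.2 of a child with an event, and the largest is 144 × (0.2120 − 0.1978) ≈ 2 children.

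**4. Restricting to therapy**

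If only events during the 5 days of treatment are counted, Day 6 closes the window for every child. Scheduled ascertainment is then equal and the ratio is 1.

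**The case against.** The strongest reply is that the safety endpoint is already confined to therapy, and Visit 3 follows the end of dosing for every child. For that endpoint the concern disappears. This stands, but it does not settle the matter, because neither the Samples text nor Safety parameters carries the limit into the analysis.

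A reader might infer that safety recording stops at Day 6 in recovered children and that their later events are lost. The documents do not support that. The Samples text considers events throughout the study, so spontaneous reports can still be recorded. The Day 14 call asks every family about condition, complications, antibiotics and concomitant therapy, and complications and hospitalization form a 14-day secondary endpoint in all children. What differs is one scheduled active check.

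A reader might also infer that Ergoferon is bound to look safer than it is. That would need a real difference in persisting illness, events counted beyond therapy, events continuing after dosing, and little captured on Day 14. Visit 4 is also not the same as non-recovery: any remaining symptom or a complication triggers it, whereas the primary endpoint counts a child as recovered with a total score of up to 3 points. The link between treatment effect and attendance is therefore looser than step 3 assumes.

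Finally, the document calls itself a protocol summary, and a fuller adverse-event section may exist elsewhere. That is a reason to word this as a request to reconcile and clarify.

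**Conclusion.** The point holds in a limited form. Scheduled safety evaluation after Day 6 depends on the course of the illness, none is marked at the one later contact that every family has, and the sections do not agree on the period over which adverse events are counted. If events beyond therapy are tabulated and the arms differ in persisting illness, the slower-recovering arm's count could be inflated by about 2 to 9%, or at most about two children per arm in the cases of step 3. Those figures rest on assumed attendance, recovery times and event rates, none of which the plan supplies. With events restricted to therapy, the effect is nil. It is a modest weakness in ascertainment and does not invalidate the safety analysis, but safety is part of the trial's stated objective and the correction is cheap enough to make.

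**What to change.** 1. Reconcile Safety assessment, the Schedule of study procedures, Samples and Safety parameters so that they state one adverse-event collection and analysis period, with an end date, for all children.
2. Mark safety evaluation at Visit 5 and add an adverse-event question to the Day 14 call, including the outcome of any event still open at Visit 3.
3. Make the between-arm comparison of adverse events over a common window, from first dose to Visit 3. Tabulate events to Day 14 additionally, and identify those first found at Visit 4.

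The cost is one question in a call already made to every family and one extra table. No visit is added, and the sample size and treatment are unchanged.

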## Statistical Analyses

### *Samples*

*Total set:* all patients included in the study whose parents/adoptive parents signed the Informed Consent Form for the patient's participation in the study. All AEs will be considered throughout the study for this sample.

*Safety population:* all patients who received at least one dose of the test drug. This sample will be used to **analyze the study therapy safety**, since all the AEs detected in the patient after administration of the drug product will be recorded. The AEs registered in patients of the *Total set* sample from the moment of signing the Informed Consent Form, but before the test drug administration will not be taken into account when analyzing the study therapy safety.

*Full Analysis Set.* This sample includes all the enrolled patients, except for those who have experienced at least one of the following events:

- 1) non-compliance with inclusion / exclusion criteria ;
- 2) the patient has not taken a single dose of the study drug;
- 3) lack of any data of the patient following randomization.

This sample, the most consistent with the "Intention-to-treat" principle, will be used for the **Intention-to-treat analysis (ITT analysis) of the the study therapy efficacy**.

To fill in the missing data (indicators/options), the method "LOCF" (Last Observation Carried Forward)" will be applied.

*Per protocol set.* This sample includes all the patients who have received the complex therapy under the Protocol, completed all the scheduled visits and had no significant deviations from the Protocol. This sample will be used for the **Per Protocol analysis (PP- analysis) of the the study therapy efficacy**.

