## **Endpoints**

### **Primary endpoint**

1. Time to alleviation of all ARVI symptoms (time from enrollment in the study to alleviation of all ARVI symptoms, according to the patient's diary).

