### **Secondary endpoints**

1. Time to normalization of body temperature.
2. Time to alleviation of flu-like nonspecific symptoms.
3. Time to alleviation of respiratory symptoms.
4. Flu-like nonspecific and respiratory symptoms total score (TS) for days 2-6 (according to the patient's diary).
5. ARVI severity (based on the area under the curve of TS for days 2-6, according to the patient's diary).
6. Percentage of patients recovered on day 2, 3, 4, 5, and 6 (according to the patient's diary).

---

 Criteria of alleviation of all ARVI symptoms: body temperature  $\leq 37.5^{\circ}\text{C}$  for 24 hours (without subsequent increase within the observation period) + absence of ARVI symptoms /presence of ARVI symptoms with  $\leq 3$ -point of TS.

 Oral temperature  $\leq 37.5^{\circ}\text{C}$  for 24 hours (without subsequent increase within the observation period).

 Absence of flu-like nonspecific symptoms/presence of one mild flu-like nonspecific symptom.

 Absence of respiratory symptoms/presence of one mild respiratory symptom.

7. Rates of antipyretic use per patient during days 1 to 5 of therapy (according to the patient's diary).
8. Percentage of patients with worsening of illness (ARVI complications, including those requiring antibiotics; hospitalization) for 14 days.

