### **Study design**

Study design: multicenter double-blind placebo-controlled randomized clinical study in parallel groups.

The study will enroll patients of either gender aged from 6 months to 6 years old with clinical manifestations of ARVI within the first day after the onset of the disease. Patients will be included evenly (1:1 ratio) in accordance with the age group: 6 months – 3 years 11 months 29 days; 4 years – 6 years 11 months 29 days. Signed information sheet for parents/adopters (informed consent form) will be obtained from all participants' parents/adopters prior to the screening procedures.

Medical history, thermometry, patient examination by a doctor, assessment of ARVI symptoms severity, and nasopharyngeal swabs will be performed at screening visit (Day 1). If the inclusion criteria are met and exclusion criteria are absent, the patient is included in the study.

Nasopharyngeal swabs will be analyzed by real-time reverse transcription polymerase chain reaction (RT-PCR) to identify the most common respiratory viruses, including (1) Influenza A virus; (2) Influenza B virus; (3) Influenza A (H1N1)pdm; (4) Human metapneumovirus; (5) Human respiratory syncytial virus; (6) Human rhinovirus; (7) Human adenovirus; (8) Human bocavirus; (9) Human parainfluenza virus 1; (10) Human parainfluenza virus 2; (11) Human parainfluenza virus 3; (12) Human parainfluenza virus 4; (13) Human coronavirus OC43; (14) Human coronavirus 229E; (15) Human coronavirus HKU1; (16) Human coronavirus NL63.

Patients are randomized into one of two groups: the 1st group patients will take Ergoferon according to the dosage regimen for 5 days; the 2nd group patients will take Placebo according to the dosage regimen of Ergoferon for 5 days.

Patient's parents/adoptive parents are provided with diaries where daily in the morning and at night they record oral temperature (measured by a digital thermometer provided by Sponsor), symptoms of ARVI (according to the 4-point scale), administered drug and concomitant therapy. Doctors instruct parents/adoptive parents how to fill in diaries; the first scores of ARVI

symptoms severity and oral temperature are made by doctors together with the parents/adoptive parents.

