### **Criteria for Withdrawal or Termination**

1. Inability or refusal of patient or parents/adoptive parents to comply the Protocol requirements.
2. Necessity in medical products prohibited within the study.
3. Development of adverse event requiring product cancellation.
4. Desire of patient or parent/adoptive patient to complete the study ahead of schedule due to inefficacy of therapy or any other reason.

---

 Criteria of severe influenza/ARVI (RF MH, 2009, 2014; Union of Pediatricians of Russia, 2014; WHO 2011; CDC 20013-2014): extreme severity of disorder (toxic shock syndrome III, critical general condition disorder, decreased activity or weakness up to complete adynamia, irritability/cry when touched, lethargy, drowsiness/longer sleep, lack of eye contact during examination, refusal to eat or drink, severe tachycardia/bradycardia, tachypnea, hypo- or hyperventilation, microcirculation disorder, peripheral cyanosis, slower capillary filling of the nailfold, continuous vomiting, signs of dehydration, decreased diuresis/anuria, convulsions, symptoms of meningism), hemorrhagic syndrome (nosebleeds, petechiae on the skin and mucous membranes), hemodynamic instability, severe obstructive disorders (stenosing laryngotracheitis, bronchial obstruction syndrome), acute respiratory failure, primary and secondary pneumonia. Risk factors for severe influenza/ARVI and development of complications are chronic diseases of the cardiovascular system, respiratory system, diabetes mellitus, immunodeficiency conditions, and cancers.

5. Cases not specified by the protocol when, according to the investigator's opinion, further participation in the study harms the patient.
6. Incorrect inclusion of ineligible patient.

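### LOCF is applied to all missing FAS efficacy data, including the diary time to alleviation, and no censoring rule is stated

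*Combined protocol and SAP*

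**What the plan says.** Under Statistical Analyses, Samples, the Full Analysis Set paragraph states: "To fill in the missing data (indicators/options), the method 'LOCF' (Last Observation Carried Forward)' will be applied". No endpoint, reason for missingness or time limit is excepted. This set carries what the plan calls its ITT efficacy analysis.

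The primary endpoint is "time from enrollment in the study to alleviation of all ARVI symptoms", taken from the diary. Footnote 1 requires a temperature at or below 37.5 °C "for 24 hours (without subsequent increase within the observation period) + absence of ARVI symptoms /presence of ARVI symptoms with" a total score of at most 3 points. Secondary endpoints 4 and 5 are the diary total score on Days 2-6 and its area under the curve (AUC).

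Parents keep the diary twice a day: "daily in the morning and at night they record oral temperature". They hand in diaries, "which parents/adoptive parents return back at Visit 3 or 4", that is on Day 6 or Day 10.

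Non-parametric criteria, item 5, lists survival analysis (LIFETEST) for the presence or absence of an event over repeated measures. It names no endpoint and gives no censoring rule.

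Reasons for withdrawal include "Necessity in medical products prohibited within the study" and a wish "to complete the study ahead of schedule due to inefficacy of therapy or any other reason".

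**The concern.** LOCF supplies a value for a measurement at a visit. Time to alleviation is an event time whose definition depends on what is recorded afterwards. Three kinds of early leaver arise:

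- **Ill at the last record.** The carried values keep the child ill to the end of the fill, and the plan does not say whether that is Day 6 or Day 10.
- **Well for less than 24 hours at the last record.** The carried values complete the 24-hour window, so recovery is confirmed on readings nobody took.
- **Well for 24 hours at the last record.** The window was recorded, but the condition of no later rise is unobserved from then on.

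For scores that fall as the illness resolves, a carried score overstates illness in a child who leaves while improving.

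At stake are power in the FAS analysis and, if dropout differs between arms, its type I error. A link between leaving and outcome is plausible because inefficacy and need for a prohibited drug are both reasons to withdraw. Without a stated horizon or censoring rule, two analysts could also code the same child differently.

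**Working it through.** **Plan's own figure.** Inputs from the sample-size section: difference 0.5 d, SD 1.3 d, two-sided 5%, power 80%. With the usual factor 2, n = 2 × 1.3² × (1.960 + 0.842)² / 0.5² = 106.1, so 107 per group. The noncentral t gives 79.97% at 107 and 80.3% at 108, so 108 is reproduced. Then 216 / (1 − 0.25) = 288. The sizing is not in dispute here.

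**Simulation.** From the plan: SD 1.3 d, effect 0.5 d, 144 per arm. Assumed: gamma times, placebo mean 4.5 d, half-day grid (twice-daily diary). There were 10,000 trials per scenario, tested two-sided at 5%. In each pair, the first figure is leaving uniformly over days 0.5-6 and the second is every leaver going before alleviation. Mann-Whitney power without dropout is 91.0%.

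| Leaving, each arm | LOCF to Day 10, Mann-Whitney | LOCF to Day 6, Mann-Whitney | Right-censored, Gehan-Wilcoxon |
|---|---|---|---|
| 5% | 89.1 / 83.6 | 89.8 / 85.9 | 91.2 / 89.5 |
| 10% | 86.1 / 76.2 | 87.9 / 81.9 | 90.1 / 89.2 |

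Loss in points against censoring:
- 5% leaving: 91.2 − 89.1 = 2.1 and 89.5 − 83.6 = 5.9 (Day 10); 1.4 and 3.6 (Day 6).
- 10% leaving: 4.0 and 13.0 (Day 10); 2.2 and 7.3 (Day 6).

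Repeat simulations of the Day 10 fill at 5% gave 86-88 / 83-84%, so single points should not be over-read.

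**Children affected.** 144 × 5% = 7.2 leavers per arm. Of these, 4.8 / 7.2 are ill at the last record. Under uniform leaving, 1.1 are well for less than 24 hours.

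**Smaller FAS.** The 25% allowance also covers screening exclusions, so the FAS size is not fixed. At 5% leaving:
- 126 per arm: 84.3 / 78.9 (Day 10), 85.4 / 81.5 (Day 6), 86.6 / 85.5 censored.
- 108 per arm: 78.7 / 73.3 (Day 10), 79.6 / 75.8 (Day 6), 81.4 / 80.1 censored.

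**Type I error.**
- Equal dropout: 4.6-5.3%.
- Assumed 10% placebo versus 5% Ergoferon: 6.8 / 11.7 (Day 10), 5.7 / 8.1 (Day 6), 4.7 / 5.0 censored.
- Reversed: 7.4 / 11.5, 5.9 / 8.1, 5.2 / 5.7.

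The inflation therefore appears whichever arm loses more children. Placebo means from 3.5 to 6.0 d gave 6-12% (Day 10), 5-10% (Day 6) and 4.7-5.8% censored under 10% placebo versus 5% Ergoferon.

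**Which test.** The plan switches to Mann-Whitney if the Kolmogorov-Smirnov check fails. On the fixed half-day grid the check rejected in every simulated trial at 144 per arm. With enrolment spread over the day, or with continuous times, it rejected in roughly 52-79%. The t-test therefore remains possible, and it loses more: 77.1 / 62.1% at 5% leaving with Day 10 fill.

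**AUC, Days 2-6.** For a score falling linearly, excess = slope × (6 − last day)² / 2. Assumed slopes of 1 or 2 points a day and a last entry on Day 3 or 2 give 4.5, 9, 8 or 16. On assumed true AUCs of 16 or 24, the range is 4.5/24 = 19% to 16/16 = 100% per leaver.

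**Skipped entries.** Suppose 24 hours needs three consecutive half-day readings and entries are missed at random with probability q; let p = 1 − q. Counting only recorded readings delays a share 1 − p³ of children. The mean delay over all children is 0.5 × [(1 − p³)/(q p³) − 3] days.
- q = 5%: 14% delayed, mean 0.16 d.
- q = 10%: 27% delayed, mean 0.36 d.

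LOCF delays only if the first well reading is missed: 5% (0.03 d) and 10% (0.06 d). Removing LOCF without a rule for skipped entries would therefore do harm on a 0.5 d scale.

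**The case against.** **Survival analysis is already listed, so censoring may be implied.** It may have been intended, but the Full Analysis Set paragraph still prescribes LOCF for the same data, and item 5 is not tied to this endpoint.

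**The harm is small in ordinary cases.** This stands. At 5% uniform leaving the loss is 1-2 points, and power at 144 per arm stays near 89-90%. Children with no data after randomization are outside the FAS, so not every leaver is filled.

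**The gain depends on the test.** This also stands. Under the assumed times, log-rank on censored data had 80.9 / 78.9% at 5% leaving, below Mann-Whitney after LOCF. Restricted mean difference had 89.7 / 88.1%. The loss figures above are against Gehan-Wilcoxon.

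Some stronger readings are tempting but not supported:
- *LOCF favours Ergoferon.* The documents give no dropout rate by arm, and the arm penalised is the one that loses more children.
- *The trial's sizing fails.* It rests on the per-protocol set, whose members "completed all the scheduled visits and had no significant deviations from the Protocol"; LOCF is not stated for that set.
- *A quarter of the FAS will be filled.* The 25% includes screening exclusions.
- *The last diary day becomes the recovery time.* The rule fills missing values; it does not turn withdrawal into recovery.
- *Normality will always be rejected.* That result follows from the assumed grid.

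**Conclusion.** The point holds for the FAS (ITT) analysis and should be fixed. As written, early leavers receive outcomes that nobody recorded, up to a horizon the plan does not state, and no censoring rule replaces this. With equal dropout the cost is power: 1-2 points at 5% uniform leaving, up to about 6 points at 5% and 13 at 10% if all leave while ill (144 per arm, Mann-Whitney after LOCF against Gehan-Wilcoxon with censoring). Under an assumed 10% versus 5% imbalance, type I error is about 7/12% (Day 10 fill) or 6/8% (Day 6 fill), against about 5% with censoring.

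These sizes rest on assumed gamma times, a 4.5 d placebo mean, a half-day grid and assumed leaving rates; only the SD, the effect and the group size come from the plan. Neither the presence nor the direction of bias can be fixed from the documents. The AUC excess per leaver, 19-100%, is an assumption-dependent range and not an estimate.

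**What to change.** In Statistical Analyses, Samples:

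1. Remove LOCF for the time-to-event endpoints, and for total score and AUC after withdrawal.
2. Analyse time to alleviation in the FAS by Kaplan-Meier (LIFETEST, already listed). Right-censor a child not yet confirmed as alleviated at the last completed diary entry. Count a child with 24 recorded well hours and no recorded later rise as an event, and state that later relapse is unobserved in those who leave.
3. Add a separate rule for isolated skipped entries. For example, a single missed entry between two recorded entries that both meet the criterion does not break the 24-hour window.
4. State the diary horizon and name one between-group test in advance: Gehan-Wilcoxon, log-rank or restricted mean difference. The choice is the sponsor's.
5. Analyse Day 2-6 total score with a mixed model on observed scores (MIXED, already listed) and derive AUC from it.
6. Add one sensitivity analysis that counts withdrawals for inefficacy or a prohibited drug as not alleviated through the diary horizon. Keep it supportive: holding all leavers as ill to Day 10 gave a type I error of 6.5 / 11.6% under the 10% versus 5% imbalance.

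The cost is SAP wording and some programming; no visit, procedure or sample size changes. Censoring assumes that leaving is unrelated to later recovery, which item 6 examines. In one check where the slower half were three times as likely to leave, all before alleviation, Gehan-Wilcoxon kept 90.3% power at 5% leaving and 4.9% type I error at 10% versus 5%.
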